Attachment 1 presents the study intervention and incentive time line.

Retention Procedures The following procedures are designed to minimize loss of potential enrollees or data from these enrollees:

- a) From the point of enrollment, WWHF will track expected due dates and follow-up with the prenatal FB provider for any delivery where they have not received notification of delivery 14 days after the expected due date. This will address the potential loss of enrollees in the transition between the prenatal FB provider counseling and the start of postnatal counseling by the WWHF staff.
- b) There will be reminder calls (up to 5 attempts) about 2 days before every in-home visit.
- c) For each missed in-person visit, WWHF staff will make proactive calls to the participant to reschedule.
- d) For each of the telephone counseling sessions, WWHF staff will make 5 call attempts for each scheduled call, providing participants with encouragement to return the call.
- e) If the woman is not home for a scheduled home visit, and does not reschedule it, the WWHF will make an additional effort to track/contact her by phone (with reminders of

the visit payment she will receive for attending) and, if that fails, by letter and contact with people whose names were given as contacts at enrollment.

- f) If the appointment is not completed within 4 additional weeks, this visit will be closed and the participant will not be compensated. An additional call will be made letting the person know the window for that visit was passed; if no phone contact can be made in three weeks, other contacts (people listed by the participant who will know her location) will be contacted. If this fails, a letter will be sent confirming that this visit is closed and encouraging the participant to contact the WWHF office.
- g) Prompt payment of participants is a key variable in retention. WWHF will disperse the incentive payments; payments will be in the form of a \$20.00 Walmart gift card. Enrollment gift cards will be mailed. They will be distributed in-person, at the completion of each home visit/CO test.

Procedures for incarceration While the study does not target incarcerated individuals, incarcerations during the period of study involvement are anticipated within the population being recruited for this study. The study has made the following procedural accommodations for this: If an individual is reported to have been incarcerated, all study involvement during the period of confinement will be suspended. No contact will be made with (and no data will be collected from) the individual during any period when they are incarcerated. The appointments during the incarceration will be recorded as missed. If the length of incarceration is known and the individual becomes available in the community again, scheduled study contacts will recommence at that time. Follow-up appointments and/or calls that are scheduled subsequent to a period of incarceration may occur. If there is no indication of when the individual will be available again, study contacts will be recorded as missed and attempts to contact will start again at the next scheduled contact. Incarcerations will not be reported to the IRB unless the above protocol has not been followed.

E. Safety Monitoring Plan

Participant risks are minimal. No drugs are used in this study. The pre-natal smoking cessation counseling services (Frist Breath) provided as part of the project have been used with this population throughout Wisconsin for 15 years. No adverse effects have been documented. The services provided postpartum are commonly used cessation/relapse prevention counseling strategies. They were used previously in STQ without any adverse effects. Participants may be experiencing more stress than normal because they are at home with a new born. In this context, smoking relapse may produce some emotional upset. All the health educators are trained to recognize this and are prepared to provide support and/or mobilize community resources as needed. There is a risk for inadvertent breach of confidentiality. This risk will be highlighted in the consent procedures.

F. Collected Information

Some information is provided to WWHF by FB sites when women enroll in FB and again at the end of their standard services to the enrolled women. All other assessment data gathered from participants will be obtained by telephone or in person by WWHF staff. These include:

- a) Baseline assessment. This survey takes approximately 10 minutes to complete and is administered by WWHF staff at the time of enrollment and after verbal consent or during a separate call if the study participant cannot complete it during this initial call. Variables collected include: motivation and confidence to quit/reduce smoking; smoking history; current smoking; barriers to cessation; past quit attempts; general health information and goals; and perceived social support (via the Wisconsin Social Support Scale).
- b) CO test for STQ participants only at the first postpartum visit
- c) CO test at the 6-month postpartum follow-up in-home visit for both STQ and FB (primary outcome)
- d) Brief survey (10 minutes) administered at the 6-month postpartum follow-up in-home visit. This survey collects information such as smoking status at delivery and at one-month postpartum as well as re-measures some of the variables collected at the baseline assessment. Also measured will be: adoption of smoke free strategies; self-efficacy to remain smoke free; motivation to remain smoke-free; time to relapse, perceived support from others; and birth outcome.
- e) WWHF staff will also record information about pertaining to conducting the study. This information includes: screening/informed consent results; participation in treatment services; counseling delivered information; and ending study prior to completion

Attachment 2 lists all the information that will be contained in the study data set.

G. Data Security

Data collected in the home are entered into SurveyGizomo, (online software). Survey Gizomo is HIPPA compliant and has Safe Harbor certification. Data is encrypted and hyperlinks are secure. The research database will be housed at WWHF. It will be stored on a computer with password access controlled by WWHF. Only WWHF staff approved to work on this study will have access. Following conclusion of the study, all research data will be cleaned and verified and then placed in a de-identified data set for analysis. UW-CTRI will assist WWHF with data analysis. To facilitate this, the de-identified database will be provided to UW-CTRI by secure FTP. Study records will be kept for seven years.

G. Data Analysis Plan

Aim 2: Is Striving to Quit more effective in achieving postpartum smoking cessation than “First Breath,” the current standard of care for pregnant women in Wisconsin who smoke?

- a) Results from screening and enrollments will be analyzed to assess the representativeness of the study sample to make inferences regarding the reach of the project among the target population.
- b) Groups A (FB) and B (STQ) will be compared on the various background and smoking variables to test the assumption that random assignment resulted in equivalent groups. Inferential statistics will be used to compare the two groups, Chi Square for nominal background/demographic data such as health insurance status and race and t-tests for interval data such as age. These variables will also be used to describe the sample using

descriptive statistics. These variables will be used as co-variates in the analysis of the primary outcome, smoking abstinence.

- c) The primary outcome is biochemically confirmed reports of abstinence for the past 7 days (i.e., 7-day point-prevalence abstinence) at six months postpartum. Biochemical confirmation will be accomplished with exhaled breath carbon monoxide (CO) testing. Experience with First Breath suggests that about 20% of all women receiving services will be abstinent at 6 months postpartum after receiving prenatal services only (vs. the 30% pregnancy abstinence rates). When tested using research protocols, STQ found that 40% were smoke free at 6 months. Because we anticipate that this rate will be lower when implemented in real world settings, we use an estimated 36% rate for power calculations. With 125 participants in each condition and two tailed alpha set at .05, we have .81 power to detect this hypothesized effect size difference (36% vs. 20%). The intent-to-treat principle will be used so that non-ascertainment (i.e., failure to attend the Follow-up Visit or a lack of a confirming carbon monoxide value) will be treated as a non-abstinent outcome. Logistic regression will be used to analyze the effect of treatment status (FB vs. STQ) on the binary abstinence outcome, and models will be run both with and without covariate adjustment. We predict that STQ will produce higher abstinence rates at 6-months postpartum than FB.
- d) Other variables collected at the 6-month postpartum follow-up visit are secondary outcomes. These include time to relapse, motivation to quit/remain quit, confidence about quitting/remain quit, and birth outcomes. Some of the secondary outcomes will be continuous for which linear regression will be used. Demographic variables will be used as co-variates in these analyses. The Benjamini-Hochberg approach will be used to control experiment-wise error for secondary outcomes. Meaningful missingness is likely for variables collected at the 6-month postpartum home visit. For such variables, we assume missingness to be nonignorable. We will model or treat missingness in several ways. For instance, we will conduct sensitivity analyses with different assumptions about the relation of missingness to actual unobserved values, which will provide explicit modeling of the impact of missingness assumptions on results. We will also use multiple imputation methods appropriate for nonignorable missing data (for both continuous and binary data) and will generate imputation models that reflect different assumptions about the missing data mechanism. Missing data, due to drop out or otherwise, it will be recorded and its causes will be noted. Relevant information will include reasons for dropout, who made the decision to drop out, and what type of participation was withdrawn (e.g., termination of intervention, refusal to complete survey, etc.).

Aim 1 and Aim 3

First Breath Providers Discussion Groups. The discussion groups will be recorded. Recordings are transcribed verbatim and entered into SurveyGizmo (SG). Transcriptions are independently reviewed and codes developed by 3 study staff. Staff met to come to a consensus on the final list of codes. Final codes entered into SG and transcriptions are coded in SG using text analysis tool. The data is qualitatively analyzed for trends, themes, and quotes. Results will be used to develop items for the survey to FB providers.

First Breath Providers Survey. Survey responses will be analyzed using descriptive statistics (percent endorsement, measures of central tendencies, standard deviation). This survey will include several questions regarding the First Breath provider characteristics such as location,

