Attachment 2: Collected Information

Description	Study Group	Source	Purpose	Time	Variable
First Breath Enrollment Information	Both FB and STQ groups	First Breath sites	Identify eligible women	At prenatal visit	
 • Name • DOB • Expected delivery date • Contact Information • Smoking Status
Screening data	Both FB and STQ groups	WWHF research staff	Establish study eligibility	After First Breath enrollment	
 • Smoked daily in last 6 months • Willing to quit or stray quit • Willing to meet with FB provider • Willing to have phone calls and home visit • Willing to take CO tests • Willing to inform of changes in contact information • Involved in other smoking study
Screening results	Both FB and STQ groups	WWHF research staff	Results of eligibility screen	After First Breath enrollment	Not willing to be screened; screen fail (reason); not consented; enrolled
Services delivered at First Breath sites	Both FB and STQ groups	Fist Breath sites	Compare groups	At end of services provided at First Breath sites	Number of counseling sessions delivered
Baseline survey (phone)	Both FB and STQ groups	WWHF research staff (Health Educators)	Compare groups	At enrollment	Participant Self-Report: 
 • Race/ethnicity • Income • Education • Employment status • Relationship Status • # in Household

					
 • # Smokers in Household (smokers/nonsmokers) • Smoking history • Smoking status (Current) • Nicotine dependency • Confidence to quit/remain quit • Motivation to quit/remain quit • Perceived support • Perceived stress • Major stressors • Mental health and SUD status • ETS exposure • Quit goals
CO measurement (Home visit)	STQ group only	WWHF research staff (Health Educators)	Provide feedback regarding quit progress	1 month postpartum	CO value
Session content	STQ group only	WWHF research staff (Health Educators)	Describe services delivered to STQ participants	Every scheduled phone call and home visit, including 6 month follow-up	
 • Did visit take place • Duration • Topics discussed

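### Secondary scales analysed as continuous are adjusted for demographics only, not for their own baseline score, which may cost some precision

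*Combined protocol and SAP*

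**What the plan says.** Item d) under Aim 2 in the Data Analysis Plan defines the secondary outcomes broadly: "Other variables collected at the 6-month postpartum follow-up visit are secondary outcomes". It names motivation and confidence among them. On the model it says "Some of the secondary outcomes will be continuous for which linear regression will be used", and on the covariates "Demographic variables will be used as co-variates in these analyses".

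Item b) describes a wider set of background and smoking variables, but assigns it elsewhere: "These variables will be used as co-variates in the analysis of the primary outcome, smoking abstinence".

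Attachment 2 lists confidence, motivation, perceived support and perceived stress for both groups in the baseline survey and in the six-month survey. Confidence carries the same label at both times, "Confidence to quit/remain quit", and so does motivation. Nowhere does the plan enter a scale's own baseline value as a covariate or specify change scores.

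**The concern.** When a scale is measured before randomisation and again at follow-up, its baseline value is often the best single predictor of the follow-up value. Leaving it out of a linear model wastes information already in hand. In a randomised comparison with outcomes observed, this causes neither bias nor type I error inflation. What is at stake is the width of the confidence intervals.

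That matters somewhat here. The sample was sized on the abstinence outcome, no power is stated for any secondary scale, the secondary tests are subject to Benjamini-Hochberg control, and losses at six months are expected.

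The point applies only to scales scored as continuous that have a matching baseline. It does not touch time to relapse, birth outcomes, binary outcomes or the primary outcome. Missing six-month outcomes are a separate matter that item d) addresses, and baseline adjustment would not solve it.

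**Working it through.** **The plan's own figure.** The only power figure is for the primary outcome: 36% against 20%, 125 per arm, two-sided 0.05, stated power 0.81. With pooled variance under the null:

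- Null standard error: √(2 × 0.28 × 0.72 / 125) = 0.0568.
- Alternative standard error: √((0.20 × 0.80 + 0.36 × 0.64) / 125) = 0.0559.
- Power: Φ((0.16 − 1.96 × 0.0568) / 0.0559) = 0.808.

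The figure reproduces, and this point does not affect it.

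**Inputs for the secondary scales.** None of these is in the documents; all are assumed.

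- r, the correlation between baseline and six-month score given the demographics: 0.2 to 0.7.
- N = 200 observed (100 per arm).
- p = 8 demographic covariates.
- q, the share of baselines recorded before randomisation: 1, 0.5 or 0.2.

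**Formula.** Relative to the demographics-only model, the variance of the treatment estimate is

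(1 − q r²) × (N − p − 3) / (N − p − 3 − m),

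where m is the number of added terms: 1 when q = 1, and 2 when q < 1, because a missing-baseline indicator is then needed. With N − p − 3 = 189, the degrees-of-freedom multipliers are 189/188 and 189/187.

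| r | q = 1 | q = 0.5 | q = 0.2 |
|---|---|---|---|
| 0.2 | 0.965 | 0.990 | 1.003 |
| 0.3 | 0.915 | 0.965 | 0.993 |
| 0.5 | 0.754 | 0.884 | 0.960 |
| 0.7 | 0.513 | 0.763 | 0.912 |

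As an example, r = 0.5 and q = 1 gives 0.75 × 189/188 = 0.754. Taking square roots for q = 1, interval widths are multiplied by 0.982, 0.956, 0.868 and 0.716, so they narrow by 2%, 4%, 13% and 28%. At r = 0.2 and q = 0.2 the variance rises by 0.3%. A simulation with 8,000 runs per cell gave variance reductions within 1.3 percentage points of these values, with both estimators unbiased.

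**In terms of power.** With all 125 per arm observed, the effect with 80% power without the baseline covariate is (1.960 + 0.842) × √(2/125) = 0.354 SD. If every baseline precedes randomisation, and ignoring the small degrees-of-freedom cost, adjustment raises power for that effect to 0.816, 0.836, 0.899 and 0.975 at r = 0.2, 0.3, 0.5 and 0.7.

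**Why q may be below 1.** Section D, Study Activities, lists randomisation within step a) and baseline collection as step b). Section B lets the baseline be done on the initial call or later. The order is therefore open.

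**What a late baseline would do.** If baselines taken after randomisation shift by 0.2 SD in one arm (assumed), adjusting for them biases the treatment estimate by −0.2 × r, which is −0.04, −0.06, −0.10 and −0.14 SD. Simulation (4,000 runs) gave −0.039, −0.060, −0.098 and −0.142. The planned model, without the baseline, showed a bias of at most 0.002.

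**The case against.** The strongest reply is that the planned model is valid and the benefit depends on three unverified facts: that the scales are scored as continuous, that the two measurements match, and that the baseline precedes randomisation. All three doubts are fair.

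- **Scoring.** Item d) says only that some outcomes are continuous, without saying which.
- **Matching.** Section F, Collected Information, words the baseline items as "motivation and confidence to quit/reduce smoking" but the six-month items as "self-efficacy to remain smoke free; motivation to remain smoke-free". It names the support instrument only at baseline: "perceived social support (via the Wisconsin Social Support Scale". Item d) of that section also lists self-efficacy, motivation and support after, and apart from, its statement that some baseline variables are measured again. Attachment 2's identical labels for confidence and motivation point the other way, but labels are not instruments.
- **Correlation.** Enrolment takes both current smokers and women who have already quit, and the Background reports at least 30% quitting by the third trimester and postpartum relapse approaching 85%. A score given in pregnancy may predict the six-month score only weakly, so the higher values of r have no support in the documents.
- **Timing.** The bias from late baselines is a risk that careless adjustment would introduce and the planned model avoids.

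These doubts limit the likely gain and explain the conditions attached to the remedy. They do not show that the baseline value is in the model. Two other defences are weaker. A confidence, motivation or stress score is not ordinarily a demographic variable. The planned multiple imputation might use baseline scores, though the plan does not say so, and that would not put them in the analysis model.

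**Conclusion.** The concern holds, as an optional improvement. For any secondary scale analysed as continuous with a matching baseline, the plan names demographic covariates only and so may give up precision.

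On the stated assumptions, the variance saving is 3% to 49% if all baselines precede randomisation, 1% to 24% if half do, 0% to 9% if a fifth do, and nil if none do. At r of 0.2 to 0.3 it is small throughout. Validity with outcomes observed, the primary analysis and its stated power are unaffected.

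**What to change.** In item d), for each secondary outcome analysed as continuous that has a matching baseline measure, add that measure's baseline value to the linear regression, alongside treatment and the planned demographic covariates. With it:

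- State which scales are scored as continuous, and confirm scale by scale that the baseline and six-month items match.
- Use only baseline values recorded before randomisation. WWHF staff run both steps, and the documents do not say they are unaware of the allocation.
- Treat any other baseline value as missing, for example with a missing-value indicator as in the calculation above.
- If few baselines precede randomisation, keep the planned model.

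The cost is one or two sentences in item d), a short check of the questionnaires, and recording the times of the baseline survey and of randomisation, which Attachment 2 does not list. No new participant data are needed, and the extra analysis work is minor.

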6-month Postpartum survey (Home visit)	Both FB and STQ groups	WWHF research staff (Health Educators)	Compare groups, measure primary and secondary outcomes	6-months post-partum	Participant Self-Report 
 • Smoking status (Current) • Confidence to quit/remain quit • Time to relapse (if applicable) • Motivation to quit/remain quit • Quitting/reduction strategies used • Perceived support • Perceived stress • Major stressors

					
 • Household smoking • ETS exposure • Breastfeeding initiation/duration • Maternal/child health outcomes • Barriers and helpful factors (open-ended) 
HE Documentation:
 
 • CO Result
Case summary (Home visit)	STQ group only	WWHF research staff (Health Educators)	Describe impact on STQ participants	6 months postpartum	
 • Total minutes of counseling • Level of engagement • Difficulty to reach/complete appointments • Number of times address changed • Referral to Wisconsin Tobacco Quit Line (WTQL) • Education to support people • Support people referred to Texting program • Support people referred to WTQL • Topics covered • Qualitative case summary
Study status	Both FB and STQ groups	WWHF research staff	Track participants through study	End of study	Unable to locate; withdrew by participant; withdrew by experimenter; unknown; completed study

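### Benjamini-Hochberg is said to control experiment-wise error for the secondary outcomes, but it controls the false discovery rate, and the plan gives neither its level nor a listed family

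*Combined protocol and SAP*

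**What the plan says.** The multiplicity rule is one sentence in the Data Analysis Plan, Aim 2, item d: "The Benjamini-Hochberg approach will be used to control experiment-wise error for secondary outcomes". Nothing else in the document qualifies it, and the false discovery rate is not mentioned anywhere.

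The same item defines the family by a rule: "Other variables collected at the 6-month postpartum follow-up visit are secondary outcomes". It then gives examples: "These include time to relapse, motivation to quit/remain quit, confidence about quitting/remain quit, and birth outcomes". Attachment 2 describes the purpose of the 6-month survey as "Compare groups, measure primary and secondary outcomes" and itemises its contents.

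A significance level appears only in item c, in the power statement for the primary outcome: "With 125 participants in each condition and two tailed alpha set at .05". No level is given for the secondary outcomes.

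**The concern.** The sentence pairs a procedure with an error rate that it does not control in general. Benjamini-Hochberg holds the experiment-wise rate when every null hypothesis is true. It has no such guarantee when real effects and true nulls are mixed, because each real effect that is rejected relaxes the threshold the remaining nulls must meet.

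The mixed case is plausible here. The plan predicts higher abstinence with Striving to Quit, and time to relapse, motivation and confidence are close to abstinence in content. Other 6-month items, such as birth outcomes, may well show no effect.

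A reader who takes the sentence at face value would treat each significant secondary result as protected against any false claim in the family. The trial is meant to persuade stakeholders to fund system changes, so that reading could matter.

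The procedure's cutoffs also depend on the level and on the number of tests, and the plan fixes neither.

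**Working it through.** **Inputs from the plan.** 125 per arm; 36% vs 20%; two-sided 0.05 (primary outcome only); stated power .81.

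**Assumptions.** Level 0.05 for the secondary family; number of tests; number and size of real effects; equal correlation between outcomes. The plan gives none of these.

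**1. The plan's own figure.** On the arcsine scale, h = 2(arcsin√0.36 − arcsin√0.20) = 0.360, and z = h·√(125/2) = 2.84. Power = Φ(2.84 − 1.96) = 0.81. The pooled-variance formula gives 0.808 and the unpooled one 0.817. The stated .81 is reproduced, and z = 2.84 serves below as the benchmark for a real effect.

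**2. Size of the family.** Item d names four outcomes. The 6-month survey in Attachment 2, leaving out current smoking status, CO and the open-ended item, has 11 entries: confidence, time to relapse, motivation, strategies, support, stress, stressors, household smoking, ETS exposure, breastfeeding, and maternal/child health. Some are compound, so 11 counts entries, not tests. Section F, item d, adds further 6-month variables, such as smoking status at delivery and at one month.

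**3. A case that can be done by hand.** Take four independent tests with two real effects so strong that they are always rejected. The Benjamini-Hochberg cutoffs are 0.05·k/4 for k = 1 to 4, so the two true nulls face 0.0375 and 0.05.

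- Chance of any false rejection: 1 − 0.9625² + 0.0125² = 0.0736 + 0.0002 = 0.074 (simulated 0.074).
- False discovery rate: (2/4)·0.05 = 0.025 (simulated 0.025).
- Holm, where the smaller null p-value faces 0.05/2: 1 − 0.975² = 0.049 (simulated 0.050).
- With one true null left, its cutoff is 0.05, so the experiment-wise rate cannot exceed 5%.

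**4. Simulation.** 200,000 families per scenario, two-sided z tests. Chance of any false rejection under Benjamini-Hochberg with real effects at z = 2.84:

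| Outcomes | Real effects | Independent | Correlation 0.3 | Correlation 0.6 |
|---|---|---|---|---|
| 4 | 1 or 2 | at most 6.4% | not tabulated | 4.9–5.1% |
| 8 | 4 | 9.5% | 8.4% | 6.4% |
| 11 | 5 | 11.7% | 10.3% | 7.1% |
| 12 | 6 | 12.5% | 10.9% | 7.4% |

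Other effect sizes:

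- All nulls true: 3.8% to 5.1%.
- One null left: at most 4.5% for z from 1 to 3, reaching 5.0% at z = 5.
- Weak effects (z = 1): at most 4.7%.
- z = 2: at most 5.2% (4 outcomes), 6.1% (8), 7.1% (11) and 7.3% (12).
- z = 3: at most 6.7% (4 outcomes); 12.5% for 11 with five real and 13.2% for 12 with six real if independent, falling to 7.3% and 7.6% at correlation 0.6.

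In these runs the false discovery rate was at most 5.1% and Holm's experiment-wise rate at most 4.9%. A separate simulation with 10 independent tests, five real, gave 10.8% at z = 2.80 and 14.1% for very strong effects.

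**The case against.** The strongest reply is that this is a slip of terminology. The procedure is named and is a recognised choice for secondary outcomes. On the preferred fix it is unchanged: at a given level and family, no p-value, rejection or sample size moves. That is true, but what the secondary results may claim does change, and this is the plan's only statement of what its multiplicity rule protects.

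The second reply is that the larger figures rest on assumptions outside the documents. Much of this stands. Only four outcomes are named, and for those the excess is about 1.4 points at most at the planned primary effect, nearly vanishing at correlation 0.6. Counts of 8 and 12 are illustrative. The benchmark z = 2.84 uses all 125 per arm, because for the primary outcome a missing result "will be treated as a non-abstinent outcome". The plan itself expects missing data on the 6-month variables, so secondary effects may be weaker. At z = 2 the excess is small.

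The third reply is that the family is bounded, since item d gives a rule and Attachment 2 itemises the survey. That holds in part. The rule limits the family but does not say which entries are tested, or how compound entries are counted.

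**Conclusion.** The statement is wrong as written. Benjamini-Hochberg does not guarantee experiment-wise control when some secondary effects are real and more than one null remains. The excess over an assumed 5% runs from nothing (all nulls true, one null left, or weak effects) to about 1.4 points for the four named outcomes and 6.7 points for 11 independent outcomes with five real effects, the last two at z = 2.84. Positive correlation shrinks it. These sizes are conditional on the assumed level, effect sizes and correlations; the mislabelled error rate is not. The consequence is confined to secondary claims. The primary comparison, its alpha and its .81 power are unaffected. The correction should be made, but it does not threaten the trial's main conclusion.

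**What to change.** In item d, keep Benjamini-Hochberg, name the false discovery rate as the quantity controlled, state its level, and make no experiment-wise claim for secondary results. Add a list of the outcomes in the family, with compound entries split into the tests to be run, and fix it before the de-identified data set described under Data Security is analysed. This takes one sentence and a list. It costs no power, though it states a weaker protection than the present wording.

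If experiment-wise control is what the sponsor wants, replace the procedure with one that provides it, such as Holm. At z = 2.84 with independent outcomes and level 0.05, power per real effect then falls from 70% to 66% (four outcomes, two real) and from 67% to 53% (11 outcomes, five real).
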